	
6 consecutive Monthly visits. Each Quarterly visit will take place by the middle of the first month (<math>\pm</math> 7 days) of each calendar quarter (i.e., January 15, April 15, July 15 and October 15).
 
For patients who did not complete Study RP103-03, study visits will consist of:
 
 
• Screening Visit which may occur up to 28 days prior to Day 1.
 
• Dose Confirmation Period (Days 1-5) which includes 3 study visits over 5 days.
 
• Day 1 includes a morning study visit while the patient is fasted, with pre-dose blood samples collected for trough cysteamine and peak WBC cystine determination while the subject is still taking Cystagon®. RP103 treatment regimen begins at the clinic on the morning of Day 1, administered Q12H at a starting total daily RP103 dose equal to 70% of the Screening total daily Cystagon® dose. Patients will leave the clinic for Days 2-3 and take RP103 as instructed.
 
• Days 4 and 5 each include a morning study visit; RP103 Q12H treatment regimen continues.
 
• Quarterly Study Visits which will take place by the middle of the first month (<math>\pm</math> 7 days) of each calendar quarter (i.e., January 15, April 15, July 15 and October 15).
 
 
All patients, including those who did and those who did not complete Study RP103-03, will have an End of Study (EOS) Visit conducted within 7 (<math>\pm</math> 2 days) from the last completed study visit or from the date of decision to terminate.

Planned Sample Size:	Up to 60 patients may be enrolled. Initial sample size depends on the number of patients entering the Study from the RP103-03 Safety and Efficacy Study. Additional patients may be enrolled after all patients from Study RP103-03 have completed participation and results demonstrate non-inferiority of RP103 versus Cystagon® in reducing WBC cystine levels.
Total Number Of Centers:	Up to 10 sites in North America and Europe
Selection Criteria:	
Inclusion Criteria:
 
 
1. Male and female subjects must have completed the last visit of Study RP103-03 and be willing to continue with RP103 treatment.
 
 
OR for patients who did not complete the RP103-03 study:

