### 9.7. Clinical Laboratory Evaluations

Clinical laboratory (hematology and chemistry) and urinalysis will be performed according to the Schedule of Events (see Appendix 14.1). [REDACTED]

[REDACTED] Females of childbearing potential will provide a serum sample for a pregnancy testing during Screening at each study visit.

Clinical safety laboratory tests will be performed by a central laboratory. For patient safety, clinical laboratory samples to manage patient adverse events may be analyzed using the clinic's local laboratory. **Table 9** summarizes tests that will be performed.

The Investigator will monitor the laboratory test findings. If any laboratory test on or after the first study drug treatment is abnormal, it will be followed at the discretion of the Investigator. Abnormal laboratory tests, including ECGs, may, in the opinion of the Investigator, be considered clinically significant and, thus, constitute or be associated with an AE. In such cases, they must be reported on the AE page of the CRF. Any abnormal clinical lab that is determined not to be clinically significant will have a description of the reason for this determination documented on the lab CRF.

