- d. A minimum of 6 consecutive Monthly ( $\pm$  1 week) Visits will be conducted for all patients who completed Study RP103-03 prior to enrolling in study RP103-04. Subjects who did not complete Study RP103-03 will not attend Monthly visits.
- e. Quarterly visits will take place by the middle of the first month ( $\pm$  7 days) of each calendar quarter (i.e., January 15, April 15, July 15 and October 15) so that samples can be analyzed on the bioanalytical lab's quarterly analysis schedule.
- f. The End of Study visit will be conducted within 7 ( $\pm$  2 days) from the last completed study visit or from the date of decision to terminate.
- g. For patients that completed the RP103-03 Study, data can be obtained from the RP103-03 Screening visit.
- h. For patients that completed the RP103-03 Study, data can be obtained from the RP103-03 End of Study Visit.
- i. Physical examinations are to include standard physical assessments together with a neurological and skin examination.
- j. Clinical laboratory (chemistry and hematology) and urinalysis samples will be collected at Screening (if required) and at Monthly and Quarterly visits, thereafter and at the End of Study (EOS) visit.
- k. 12-lead ECG will be collected within 30 minutes prior to Study drug administration at Screening (if required) and at Monthly and Quarterly visits, thereafter and at the End of Study (EOS) visit. For patients that did not complete Study RP103-03, the 12-lead ECG will also be conducted at approximately 3 hours ( $\pm$  15 minutes) post RP103 dose on Day 1.
- l. Vital signs will be measured within 30 minutes prior to Study drug administration at Screening (if required) and at Monthly and Quarterly visits, thereafter and at the End of Study (EOS) visit. For patients that did not complete Study RP103-03, vital signs will also be repeated 30 minutes prior to Study drug administration on Day 1.
- m. [REDACTED]
- o. RP103 will be administered Q12H daily. Patients that completed Study RP103-03 will continue to receive their Q12H RP103 dose determined during that Study. For patients that did not complete Study RP103-03, the first dose of RP103 will be given on Day 1, with a starting Q12H RP103 dose at a total daily dose which is 70% of their total daily dose Cystagon® dose.

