The number and percentage of subjects with any treatment-emergent adverse events will be summarized by relationship to study drug (not related, unlikely related, possibly related, probably related, definitely related, unknown) and severity (mild, moderate, severe, life-threatening, death, unknown) by SOC and PT. In these tabulations, each subject will contribute only once (i.e., the most related occurrence or the most intense occurrence) to each of the incidence rates in the descriptive analysis, regardless of the number of episodes – e.g. worst grade, per subject, per toxicity.

In addition, summaries of the incidence of subjects with AEs, and SAEs, by study year of onset (Year 1, Year 2 and Year 3 or later) will be generated. Treatment-emergent gastro-intestinal adverse events, i.e. adverse events with SOC of “gastrointestinal disorders”, will also be summarized by frequency of episodes (1-3 occurrences vs 4 or more) by PT. Similarly, treatment-emergent treatment-related gastro-intestinal adverse events will be summarized.

All adverse events occurring on study will be listed in subject data listings.

By-subject listings also will be provided for the following: serious adverse events, adverse events for laboratory abnormalities, and adverse events leading to study discontinuation.

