### **9.3. Laboratory Data**

Clinical laboratory values will be expressed using SI units.

Hematology, chemistry, and urinalysis results will be summarized for each lab parameter at baseline, each collected postbaseline visit, and change from baseline using descriptive statistics (number of subjects, mean, median, SD, and minimum and maximum values). In the event of repeat values, the last non-missing value per visit, per timepoint will be used. If there are multiple records for the same visit and timepoint, the average of the values will be used.

Analysis of individual subject changes will be summarized by shift tables, which will be generated for hematology and serum chemistry parameters. These tables will show the number of subjects who had values that shifted from low, normal, or high at baseline to low, normal, or

---

high at each collected visit.

All laboratory data will be provided in data listings. Values outside of the reference range will be flagged.

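### Do the last-value and averaging rules for repeated laboratory results in SAP 9.3 conflict in a way that needs a change?

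*SAP*

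**What the plan says.** SAP 9.3 summarizes hematology, chemistry and urinalysis at baseline, at each collected post-baseline visit and as change from baseline. The paragraph ends with two selection rules. The first reads "In the event of repeat values, the last non-missing value per visit, per timepoint will be used". The second reads "If there are multiple records for the same visit and timepoint, the average of the values will be used".

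The next paragraph adds shift tables: "Analysis of individual subject changes will be summarized by shift tables, which will be generated for hematology and serum chemistry parameters". It has no selection rule of its own. The section closes by providing all laboratory data in listings, with values outside the reference range flagged.

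Note j to the Schedule of Events (Protocol Appendix 14.1) sets the sampling: "Clinical laboratory (chemistry and hematology) and urinalysis samples will be collected at Screening (if required) and at Monthly and Quarterly visits, thereafter", and again at the End of Study visit. Protocol 9.7 assigns the safety tests to a central laboratory but says that "clinical laboratory samples to manage patient adverse events may be analyzed using the clinic's local laboratory". On abnormal results that the investigator judges clinically significant, the same section says: "In such cases, they must be reported on the AE page of the CRF". SAP 9.2 plans by-subject listings that include "adverse events for laboratory abnormalities, and adverse events leading to study discontinuation".

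**The concern.** Both rules act on the same unit: one subject, one parameter, one visit, one timepoint. Two non-missing results in that unit can be called repeat values or multiple records, and the SAP does not say how the terms differ or which rule comes first. Two programmers could follow the text and produce different tables.

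Safety is the primary objective and laboratory testing is part of the safety endpoint. The choice can move a subject from one shift-table category to another as well as change a mean slightly. That the selected value also feeds the shift tables is implied rather than stated.

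**Working it through.** The plan gives no figure to reproduce, so the check has three parts: whether another section settles the overlap, whether the two sentences can be read together, and how large a difference could be.

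**1. Other sections.** SAP 4.2.1 defines baseline as the last non-missing measurement before first dose, so baseline has a rule. SAP 4.2.9 picks the assessment closest to the scheduled day, but only for Analysis Visits; laboratory tables use Collected Visits. Protocol 9.7 does not define a retest. The overlap therefore remains for post-baseline Collected Visits.

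**2. Reading the sentences together.** If averaging governed every case of several results at one visit and timepoint, the last-value sentence would never operate. If the last value governed every case, the averaging sentence would never operate. Each has content only if they address different situations. The usual pair is:

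| Situation | Rule | Value used |
|---|---|---|
| Test repeated on a new sample | last non-missing | x2 |
| Duplicate records of one sample | average | (x1 + x2)/2 |

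For results x1 then x2, the average minus the last value is (x1 − x2)/2. For identical duplicate records this is zero, so which rule is applied there does not matter. The choice matters only for a genuine retest at the same visit and timepoint, where the ordinary reading points to the last value.

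**3. How often it could arise.** The schedule has one laboratory collection per visit. The blood-volume table in Protocol 9.8 agrees: 4.5 mL for chemistry and hematology, 1.0 mL for PK and 4.0 mL for PD make 9.5 mL per visit. Then 9 × 9.5 = 85.5 mL for monthly visits and 30 × 9.5 = 285 mL for quarterly visits, both as printed. SAP 4.2.9 builds Collected Visits from the scheduled visit on the case report form and mentions unscheduled assessments only for Analysis Visits. A retest on another day therefore appears not to enter these tables unless it is recorded under a scheduled visit. That is an inference; the SAP does not say so.

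**4. Size of one disagreement (illustrative values, not from the documents).** Take an upper limit of 40, a first result of 60 and a second of 38.

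- Last value: 38, normal.
- Average: (60 + 38)/2 = 49, high.
- Difference: 49 − 38 = 11 units.

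With a first value of 60, the average exceeds 40 when the second exceeds 2 × 40 − 60 = 20, and the last value is normal when the second is at most 40. The categories therefore disagree for second values above 20 and up to 40. Checks:

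- 15 gives an average of 37.5; both rules say normal.
- 25 gives 42.5; the rules disagree.
- 45 gives 52.5; both rules say high.

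The enrolment cap comes from the Protocol Synopsis: "Up to 60 patients may be enrolled". RP103-03 completers number at most 43 randomized − 2 withdrawn = 41 (Protocol 4.2.2). If every subject in the group contributes, one such subject at one visit has this effect:

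| Group | Visit mean | Shift-table cell |
|---|---|---|
| All 60 | 11/60 = 0.18 units | 1/60 = 1.7 points |
| 41 completers | 11/41 = 0.27 units | 1/41 = 2.4 points |

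In a subgroup of n subjects the cell effect is 100/n points. The documents do not give the sizes of the young-child and transplant subpopulations. SAP 9.3 describes the shift tables as numbers of subjects, and on that scale the effect is one subject in any group.

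**The case for a change.** The strongest case for a change is that the retest-versus-duplicate reading is natural but unwritten. Protocol 11.1 promises a SAP that sets out the methods in detail, and one or two sentences would remove the discretion. The wording is also loose at the edges. Averaging has no meaning for qualitative urinalysis items such as color and turbidity (Protocol Table 9). Local-laboratory results taken to manage adverse events are not ranked against central ones. Safety output is given by subpopulation, where one subject weighs more.

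The textual point stands: the terms are undefined and no precedence is written. The rest carries less weight. Descriptive statistics for continuous data cannot be applied to color or turbidity, so no analyst would average them. Whether local results enter the laboratory dataset at all is not stated, so a clash between local and central values is conjecture. The subpopulation argument needs a same-visit retest that straddles a reference limit, and nothing in the documents shows that one occurs.

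**Conclusion.** This is a gap in wording that analysts fill sensibly, and no change to the plan follows. Either convention gives a sound descriptive summary, and the two sentences fit together once a retest is distinguished from a duplicate record. Carrying the selected value from the descriptive tables into the shift tables is the obvious course, and SAP 4.2.1 already fixes baseline.

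The effect on this trial's tables cannot be calculated without a repeat frequency. For one subject with the illustrative values it is 0.18 units on a visit mean and 1.7 percentage points on a shift cell among 60, or 2.4 points among 41 completers. These figures assume that all subjects in the group contribute at that visit.

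A safety signal would not be hidden by either rule. Both results appear in the listings with out-of-range values flagged, clinically significant abnormalities are reported as adverse events, and adverse events for laboratory abnormalities have their own by-subject listing. SAP 4.2.1 treats any statistical testing as exploratory, and the sample size comes from enrolment, so no conclusion depends on the choice.

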Study Endpoints:	
Safety Endpoints:
 
 
• The safety profile of RP103 will be investigated by safety reviews conducted by the Investigator at or prior to each Monthly or Quarterly visit and through adverse event report monitoring (including attribution of treatment-emergent adverse events and serious adverse events [SAEs]), physical examination (including basic neurological and skin assessment findings), vital signs, ECG and clinical laboratory testing as outlined in the Schedule of Events.
 
 
Pharmacokinetic Endpoint:
 
 
• The trough plasma cysteamine concentration will be measured from samples collected 0.5 hour post dose at each study visit.
 
 
Pharmacodynamic Endpoint:
 
 
• The WBC cystine content will be measured from samples collected 0.5 hour post dose at each study visit.
 
 
[REDACTED]:
 
 
• [REDACTED]
 

Duration of the Study:	
Patients will be followed until Study termination; which can occur by patient, physician or Sponsor request, or until the RP103 drug is available through the appropriate marketing approval, or until the Sponsor terminates development of RP103 for this indication for any reason. Approximate treatment time in the Study is up to 96 months. However, a subject may withdraw consent or be withdrawn from the study prior to completion.

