### **4. STATISTICAL METHODS**

#### **4.1. Sample Size Justification**

The sample size for this study is determined by the number of subjects who participated in the previous phase III Study (RP103-03) and any additional subjects, who did not complete the RP103-03 study, who enroll after all subjects that participated in RP103-03 completed and data have been analyzed.

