#### **4.2. General Statistical Methods and Data Handling**

##### **4.2.1. General Methods**

All data displays and analyses will adhere to the International Conference on Harmonisation (ICH) recommendations, and will be formatted to the appropriate page size(s).

Tabulations will be produced for appropriate demographic, baseline, efficacy, and safety parameters. For categorical variables, summary tabulations of the number and percentage within each category (with a category for missing data) of the parameter will be presented. For continuous variables, N, the mean, median, standard deviation, minimum and maximum values

---

will be presented.

Relative days will be calculated relative to the first dose of study drug. Day 1 will be the first day of study drug administration in the study, and the day prior to the first dose of study drug administration will be Day -1. There will be no Day 0.

Any statistical testing will be considered exploratory; two-sided p-values will use alpha = 0.050.

Baseline is defined, unless otherwise specified, as the last non-missing measurement before the first dose of study drug, unless otherwise specified. For subjects who completed Study RP103-03, baseline results could come from the Screening Visit (which is the RP103-03 Period 2 Day 7 End of Study (EOS) visit).

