#### 4.2.9. Visit Windows

The visit schedule in Study RP103-04 differed according to whether a subject entered the study after completing Study RP103-03 or entered the study without having previously participated in Study RP103-03 (i.e., Subjects  $\leq$  6years of age and kidney transplant recipients). This difference in visit schedule resulted in each Quarterly visit for subjects from Study RP103-03 occurring, on average, approximately 6 months later in the study than the corresponding Quarterly visit for subjects who did not previously participate in Study RP103-03. For example, the Quarterly 1 visit of a subject from Study RP103-03 generally occurred at approximately 0.75 years in the study, while the Quarterly 1 visit for a subject not previously participating in Study RP103-03 generally occurred at approximately 0.25 years in the study. Two approaches were taken in the analysis to aligning visits for summarization over time:

1. **Collected Visits:** Scheduled Visits (i.e., the visit as recorded on the case report form) were assigned to what is referred to as “Collected Visits” (see
2. Table 2). Summarization using Collected Visits will help to address the approximate 6-month difference between the Quarterly visits for subjects from Study RP103-03 compared to subjects who had not participated in Study RP103-03.

**Table 2: Definition of “Collected Visits” for Subjects Not Previously Participating in Study RP103-03 (Subjects  $\leq$  6 Years of Age and Kidney Transplant Recipients)**

Scheduled Visit		Assigned “Collected Visit” (Label)
Scheduled Visit Number	Scheduled Visit Name	
14	Quarterly 1	Monthly 3
15	Quarterly 2	Monthly 6
16	Quarterly 3	Quarterly 1
17	Quarterly 4	Quarterly 2
18	Quarterly 5	Quarterly 3
19	Quarterly 6	Quarterly 4
20	Quarterly 7	Quarterly 5
21	Quarterly 8	Quarterly 6
22	Quarterly 9	Quarterly 7
23	Quarterly 10	Quarterly 8
24	Quarterly 11	Quarterly 9

Scheduled Visit		Assigned “Collected Visit” (Label)
Scheduled Visit Number	Scheduled Visit Name	
25	Quarterly 12	Quarterly 10
26	Quarterly 13	Quarterly 11
27	Quarterly 14	Quarterly 12
Continues in this pattern for however many Quarterly visits occur		

The table only displays Collected Visits for which the name/label differs from that of the Scheduled Visit.

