#### **9.5. Electrocardiogram**

Electrocardiogram data will include heart rate, QRS duration, QRS axis, QT and PR intervals, and QT interval corrected for heart rate using Fridericia method (QTcF). ECG data will be summarized for baseline, each collected postbaseline visit and for the change from baseline to each visit using descriptive statistics (number of subjects, mean, median, SD, and minimum and maximum values) by treatment.

Overall interpretation results for the ECG are classified into 1 of 3 categories: normal, abnormal – not clinically significant, or abnormal – clinically significant. Shift tables will show the number of subjects who had results that shifted from normal, abnormal – not clinically significant, or abnormal – clinically significant at baseline to normal, abnormal – not clinically significant, or abnormal – clinically significant at each collected post-baseline visit.

All ECG data for each subject will be provided in data listings.

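### SAP 9.3 and 9.5 tabulate laboratory and ECG results only by scheduled visit, so the visible tables cannot show how many patients were ever affected

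*SAP*

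**What the plan says.** **Laboratory (SAP 9.3).** Hematology, chemistry and urinalysis get n, mean, median, SD, minimum and maximum at baseline and each collected visit, and for change from baseline. Shift tables cover hematology and chemistry only: "These tables will show the number of subjects who had values that shifted from low, normal, or high at baseline" to the same three classes at each collected visit. Two sentences deal with repeats: one takes the last non-missing value per visit and timepoint, and the next averages multiple records for the same visit and timepoint. All results are listed, with out-of-range values flagged.

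**ECG (SAP 9.5).** "ECG data will be summarized for baseline, each collected postbaseline visit and for the change from baseline to each visit", including QTcF. Shift tables use three interpretation classes: normal, abnormal but not clinically significant, and abnormal and clinically significant.

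**Collected visits (SAP 4.2.9).** "Scheduled Visits (i.e., the visit as recorded on the case report form) were assigned to what is referred to as" collected visits. The other visit definition, analysis visits, assigns results to months by date and expressly admits unscheduled assessments. SAP 8.1 and 8.2 use it for WBC cystine and plasma cysteamine. SAP 9.3 and 9.5 do not.

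**Off-schedule tests (Protocol 9.7).** Outside the central laboratory, "clinical laboratory samples to manage patient adverse events may be analyzed" at the clinic's own laboratory. The same section requires abnormal tests, ECGs included, to be entered as adverse events when the investigator considers them clinically significant.

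**The concern.** Long-term safety is the primary objective, the study has one arm, and "Approximate treatment time in the Study is up to 96 months". The basic laboratory question is how many patients developed an abnormality of a given degree at any time on RP103. A set of visit tables does not answer it. The same count of one at ten visits may be one patient ten times or ten patients once.

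Four features make this matter here:

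- Protocol 4.3 names reversible leucopenia and abnormal liver tests among occasional effects of cysteamine. A reversible effect may be present at one visit and gone by the next.
- Many patients may start outside the reference range. Protocol 4.2 describes progressive glomerular failure, Protocol 7.1 admits new patients with an estimated GFR just above 30, and SAP 3.1 has a renal transplant subgroup. A creatinine that starts high and doubles stays in the same shift cell.
- Results obtained because something looked wrong are the ones most likely to be unscheduled, and they have no stated route into these tables.
- Protocol 10.1.1 includes urine protein in one of its study-halt criteria, yet urinalysis has no shift table.

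**Working it through.** **No planned figure to reproduce.** The SAP states no rate, threshold or power for laboratory or ECG data. "The sample size for this study is determined by the number of subjects who participated in the previous phase III Study (RP103-03") and any later enrolment, and "Any statistical testing will be considered exploratory; two-sided p-values will use alpha = 0.050". The check is therefore where each kind of result goes, followed by an illustration of size.

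**Number of visits.** Protocol 9.8 gives visit maxima, and its blood-volume totals reproduce:

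- Completers of RP103-03: 1 + 9 + 30 + 1 = 41 visits, and 41 × 9.5 mL = 389.5 mL. After screening that leaves 9 + 30 + 1 = 40 visits.
- New patients: 1 + 3 + 32 + 1 = 37 visits, and 37 × 9.5 mL = 351.5 mL. After Day 5 that leaves 32 + 1 = 33 visits. The 32 quarterly visits span 32 × 3 = 96 months.

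The schedule of events still shows 5 to 6 quarterly visits, which would give 6 + 5 + 1 = 12 to 9 + 6 + 1 = 16 visits for completers. I use 32 and show the range.

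**Where each kind of result goes.**

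- *Transient abnormality present at a scheduled visit:* that visit's statistics and shift table. No table accumulates it by patient.
- *Worsening within the high class:* change from baseline, and possibly the minimum or maximum, at that visit, without patient identity. It is invisible in the shift table.
- *Result from an unscheduled visit:* the listings, and the adverse event tables if judged clinically significant. No laboratory or ECG table.
- *Repeat within one visit:* take 5 × ULN followed by 1 × ULN. The last-value rule tabulates 1 × ULN; the averaging rule tabulates (5 + 1) / 2 = 3 × ULN. Neither tabulates 5 × ULN, and the SAP does not say which rule governs.
- *Urinalysis:* some items in Protocol Table 9 are categorical by nature (blood is marked qualitative; color and turbidity are others). SAP 4.2.1 would give category counts per visit, but no change from a patient's own baseline.

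**Illustrative size.** Assumptions, none from the documents except the maximum of 60 ("Up to 60 patients may be enrolled"): all 60 stay throughout; 20% of them, 0.20 × 60 = 12 patients, have one abnormal visit each, spread evenly; the chance of a result above range is 2.5% per visit.

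- Affected patients per visit table: 12 / 32 = 0.375, about 0.4. Range: 12 / 40 = 0.3 to 12 / 12 = 1.0.
- Patients high by chance per visit table: 0.025 × 60 = 1.5.
- Chance that an unaffected patient is high at least once, if visits are independent: 1 − 0.975^32 = 0.555, about 56%. If a patient's results were perfectly correlated it would be 2.5%; positive correlation gives something between.

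The first two figures show that scattered events sit below chance background in any one table. The third shows that a plain count of patients ever above range could mislead in the other direction, which is the reason to use grades.

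**The case against.** A reader might infer that transient or within-class deterioration never reaches a table, or that these data are tabulated only by low, normal and high. The documents do not support either. Change from baseline with minimum and maximum is planned at every collected visit, a transient abnormality present at a scheduled visit enters that visit's shift table, and ECG shifts use interpretation classes.

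The strongest counter-argument is the adverse event route. Protocol 9.7 sends clinically significant laboratory and ECG abnormalities to the adverse event page without limiting this to scheduled visits. SAP 9.2 then counts each subject once per preferred term at the most severe occurrence, reports Grade 3 or higher, and lists laboratory adverse events by subject. Local-laboratory samples are by definition taken for events already under adverse event recording. This stands, and it means clinically significant abnormalities can be counted per patient. But it depends on investigator judgement, and an objective laboratory table is the usual check on that judgement.

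Three further points stand. The SAP's table list (12.1) and part of Section 8 are redacted, and eGFR is defined in the abbreviations but absent from the visible body, so a worst-value or renal table may exist; the creatinine example is the most exposed to this. The protocol's own statistical section promises only means, mean changes and flagged listings, so the SAP already exceeds it. The illustration rests on assumed rates, and a rate above range says nothing about a low value such as leucopenia.

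**Conclusion.** The point holds for the visible text of SAP 9.3 and 9.5. Those sections plan no per-patient worst post-baseline, graded or threshold summary and no urinalysis shift table. They give unscheduled values no route into the tables and state two conflicting repeat rules. The number of patients ever affected, independent of investigator judgement, cannot be read from the laboratory or ECG tables they describe. It would have to be assembled by hand from listings.

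It does not follow that the number is missing from every planned table: clinically significant abnormalities can appear in the adverse event tables, and the table list is not visible. The size, about 0.4 affected patients per visit table against 1.5 by chance, is illustrative and rests on the assumptions stated with it. No design figure changes. This is an inexpensive improvement that bears on the primary objective.

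**What to change.** **SAP 9.3.**

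- Add a baseline-by-worst-post-baseline shift table with each patient counted once per parameter. Use CTCAE grade where one exists and low/normal/high otherwise. Name one CTCAE version: Protocol 10.1 cites 3.0 and a footnote cites 4.0. Where both directions matter, tabulate low and high separately.
- Include all values obtained on RP103: scheduled, unscheduled and any local-laboratory results held in the database.
- Take the worst value among repeats for this table, and state a single repeat rule for the visit tables.
- Add category shifts for urine protein, glucose and blood.

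**SAP 9.5.** Add each patient's maximum QTcF and maximum increase from baseline, in categories stated before the analysis, with unscheduled ECGs included.

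Keep the visit tables. If the redacted list already contains such tables, the method still needs stating in 9.3 and 9.5.

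**Cost.** A few extra tables, a grading step, and separate reference ranges for local-laboratory values. The documents do not say whether local results are in the database; if they are not, the table should say so. Grades still hide change within a grade, which the continuous visit summaries continue to show.
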